2.3 MULTIVARIATE REGRESSION ANALYSES OF EFFECT-MODIFYING ROLES OF MARKERS

Following the exploration of the effect-modifying roles of the J individual marker values, multivariate models will be fitted to investigate whether there are critical combinations of levels across the markers which identify CCP which is particularly effective in reducing the odds of the primary response. For this we let M_{ij} denote the j th marker, $j = 1, \dots, J$ and $Z_i = (X_i, M_{i1}, \dots, M_{iJ})'$. Moreover we consider

$$\log \left(\frac{\pi(Z_i)}{1 - \pi(Z_i)} \right) = \beta_0 + \beta_1 X_i + \beta_2 X_i M_{i1} \cdots + \cdots + \beta_{J+1} X_i M_{iJ}.$$

and test the significance of the interaction terms $\beta_2, \dots, \beta_{J+1}$. Again generalized additive models will be explored to provide graphical displays conveying the nature of the effect-modifying role of the marker.

2.4 INCORPORATING THE PATIENT MARKER VALUES

2.4.1 EXPLORING THE EFFECT OF PATIENT MARKER VALUES

Here we consider patients in the CCP arm along but let M_{ij}^P denote the marker value for the j th marker measured in the patient, assumed to be centered. Let $Z_{ij} = (M_{ij}, M_{ij}^P)'$ for a particular marker under study. Here we consider interactions between the marker value in the transfused plasma and the marker value in the patient in models given by

$$\log \left(\frac{\pi(Z_{ij})}{1 - \pi(Z_{ij})} \right) = \theta_0 + \theta_1 M_{ij} + \theta_2 M_{ij}^P + \theta_3 M_{ij} M_{ij}^P,$$

$$j = 1, \dots, J.$$

2.4.2 INCORPORATING THE PATIENT MARKER VALUES - EFFECT MODIFYING ROLES

Let M_{ij}^P denote the marker value for the j th marker measured in the patient, as opposed to the unit transfused, $j = 1, \dots, J$. Additional analyses will introduce the patient markers denoted M_{ij}^P into the analyses, which are assumed to be centered values. Let $Z_{ij} = (X_i, M_{ij}, M_{ij}^P)'$ for a particular marker under study. Here we consider interactions between the marker value in the transfused plasma and the marker value in the patient in models given by

$$\log \left(\frac{\pi(Z_{ij})}{1 - \pi(Z_{ij})} \right) = \gamma_0 + \gamma_1 X_i + \gamma_2 X_i M_{ij} + \gamma_3 X_i M_{ij}^P + \gamma_4 X_i M_{ij} M_{ij}^P.$$

Again multivariate models involving several markers can be considered if the above marker-specific analyses yield evidence that more than one marker may be critical in determining the effect of the convalescent plasma.

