⁽⁹⁾ To be performed using frozen leftover sample or extra tube collected once at baseline and once during follow-up between 24h and 5 days post-randomization for both arms

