Donor samples will be tested for the presence of total anti-SARS-CoV-2 antibodies and neutralizing antibodies for all CCP units transfused. Moreover, there will be samples taken from

study participants to assess antibody titre at the time of randomization and 48 hours later. The results of the donor antibody testing will be used to study the effect of neutralizing antibodies on clinical outcomes. The results of antibody testing of participants will enable investigation of the effect of CCP transfusion on participant antibody levels.

The total and neutralizing antibody titres for the donor samples will be recorded. In order to assess the effect-modifying role of these titres on the outcome, we will consider regression models for the primary outcome with covariates based on treatment arm, titres and interactions terms. For the primary binary outcome, a logistic regression model will be fitted involving the treatment indicator (equaling 1 for those in the CCP arm), an "interaction term" defined as the product of the treatment indicator and the log transformed and centered total antibody titre for the plasma transfused, and a second "interaction term" defined as the product of the treatment indicator and the log transformed and centered neutralizing antibody titre for the plasma transfused. The main effect of treatment will then correspond to the effect of CCP for a unit with the geometric mean total antibody titre and the geometric mean neutralizing antibody titre. The coefficient of the first "interaction term" will reflect how this CCP effect is moderated according to the total antibody titre for the plasma sample transfused, while the second "interaction term" will reflect how the CCP effect is moderated by the neutralizing antibody titre of the plasma sample transfused; the phrase "interaction term" is in quotation marks because the main effects for these titre based variables are not included in the linear predictor.

Similar analyses to those for the total and neutralizing antibodies will be carried out incorporating information of the patients own total and neutralizing antibody profiles prior to the plasma transfusion to explore how the benefit of CCP may vary depending on the antibody profile of the recipient. These analyses will be carried out at the interim analysis for the IDSMC and at the time of study completion.

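### The recipient-antibody model in SAP Supplement 2.4.2 has no main effect for the patient's own marker, so its X × M^P coefficient measures prognosis in the CCP arm, not a change in CCP benefit

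*SAP*

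**What the plan says.** Supplement 2.4.2, whose heading announces effect-modifying roles, gives the linear predictor "\gamma_0 + \gamma_1 X_i + \gamma_2 X_i M_{ij} + \gamma_3 X_i M_{ij}^P + \gamma_4 X_i M_{ij} M_{ij}^P". X is randomization to CCP and M is the marker in the plasma. M^P is defined by the words "denote the marker value for the j th marker measured in the patient, as opposed to the unit transfused".

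SAP 4.6.1 states why recipient markers are brought in: "to explore how the benefit of CCP may vary depending on the antibody profile of the recipient". It schedules these analyses for the IDSMC at the interim and again at study completion.

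Four other places bear on the point:

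- **SAP 4.6.1, donor titres.** It puts interaction term in quotation marks "because the main effects for these titre based variables are not included in the linear predictor". That remark concerns titres of the transfused plasma.
- **Supplement 2.** The only term said to be suppressed from the printed models is the plasma provider.
- **Supplement 2.4.1.** The model restricted to the CCP arm is "\theta_0 + \theta_1 M_{ij} + \theta_2 M_{ij}^P + \theta_3 M_{ij} M_{ij}^P", which carries M^P on its own.
- **Protocol 8.3, Schedule of Assessment Events, footnote 9.** Recipient samples for anti-CoV-2 titres are "collected once at baseline and once during follow-up between 24h and 5 days post-randomization for both arms".

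**The concern.** Leaving out the main effect is right for the donor marker. SOC patients receive no plasma, so M has no value for them and only X × M makes sense. The patient's own marker is different: it is a baseline covariate that exists in both arms and can predict outcome whether or not plasma is given. Effect modification by M^P is the difference between its slopes in the two arms. A model that fixes the SOC slope at zero cannot estimate that difference.

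Protocol 1.1 gives a reason to expect antibody response to be prognostic. Protocol 1.7 cites a SARS cohort in which convalescent plasma did best in seronegative patients. If patients with more antibody fare better in both arms, the printed model will report that CCP works better as recipient antibody rises. That is the reverse of the hypothesis, produced by prognosis alone.

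**Working it through.** **Inputs.** From SAP 1.3: 800 CCP and 400 SOC patients, 30% SOC risk, 25% relative reduction (so 22.5% under CCP), two-sided α = 0.05, 80% power. From SAP 4.7: 400 and 200 patients at the interim. The prognostic odds ratio (OR) of M^P per SD is not in the documents; 0.50 to 1.00 is an assumed range.

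**The plan's own figure.** 30% against 22.5% with 400 SOC and 800 CCP gives power 0.801, and the required total comes back as 1200. The base case is reproduced. The documents give no figure for the 2.4.2 model itself.

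**Algebra.** Set X = 0 in the printed model: log-odds = γ₀ for any M^P. Set X = 1: log-odds = (γ₀ + γ₁) + γ₂M + γ₃M^P + γ₄M·M^P, which is the CCP-only model of 2.4.1 with γ₃ = θ₂. Fitted to the same simulated data, the two estimates agreed to about 1e-16. SOC marker values contribute nothing to γ₃.

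**Hand approximation.** For a standardised marker the standard error (SE) of the CCP-arm slope is about 1/√[n₁p₁(1−p₁)] = 1/√(800 × 0.225 × 0.775) = 0.0847. At a prognostic OR of 0.83 (1/1.2), |ln OR| = 0.182, z = 0.182/0.0847 = 2.15, and the chance of rejection is about Φ(2.15 − 1.96) = 58%, although there is no modification.

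**Simulation.** 1500 trials per row, the same prognostic OR in both arms, CCP effect as planned, two-sided 5% Wald test of γ₃. The provider factor was not simulated.

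| Assumed prognostic OR per SD | As printed | With M^P main effect |
|---|---|---|
| 1.00 | 5.1% | 5.3% |
| 0.91 | 20.2% | 4.1% |
| 0.83 | 58.7% | 5.5% |
| 0.77 | 84.9% | 6.0% |
| 0.67 | 99.1% | 5.2% |
| 0.50 | 100% | 4.1% |
| 0.83, interim N = 600 | 32.4% | 4.1% |
| 0.67, interim N = 600 | 90.1% | 5.7% |

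In the N = 1200 rows the mean exp(γ₃) from the printed model equals the prognostic OR to within simulation error (0.77 for 0.77, for example). With the main effect it is 0.99 to 1.00; the true value is 1.

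**No CCP effect at all.** Two separate runs at prognostic ORs of 0.9, 0.8 and 0.7 gave 27% and 31%, 80% and 80%, and 99% in both, against 4% to 6% with the term added.

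**Illustration with a yes/no marker.** Assume risks of 35% and 25% by serostatus in both arms and an even split. The spurious interaction OR is (0.25/0.75)/(0.35/0.65) = 0.62. Within 400 + 400 CCP patients, SE = √(1/91 + 1/75) = 0.156, z = 0.480/0.156 = 3.07, and rejection is about Φ(3.07 − 1.96) = 87%. Simulation gave 87% to 89% as printed and 4% with the main effect.

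**Masking.** With a prognostic OR of 0.70 and a true interaction ratio of 1/0.70, the two cancel in the CCP arm. The printed model rejects in 4.1% of trials and the corrected model in 71.4%.

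**γ₄.** The test of the donor-by-recipient term gave identical rejection rates under both models (4.4% to 5.4%).

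**The case against.** The best defence is that 2.4.2 introduces its model as a study of the interaction between plasma marker and patient marker. That is γ₄, which is unharmed, and the section prescribes no explicit test of γ₃. This stands as a limit on the damage. It does not clear γ₃, which is the only coefficient that can answer the question in SAP 4.6.1 about recipient antibody profile, and which will be read that way under the section's heading.

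Second, baseline seropositivity is already a listed subgroup (Protocol 12.4.4, SAP 4.4). Comparing arms within serostatus is not distorted by prognosis. That is true, so the question has one sound analysis. It also means the continuous-marker model could contradict that analysis for no biological reason.

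Third, the size rests on an assumed prognostic OR, the yes/no example is not the printed continuous-marker analysis, and no stopping rule uses γ₃. All true. The analysis is exploratory, but that label excuses low power and multiplicity, not a coefficient that estimates the wrong quantity.

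Fourth, the agreement of 2.4.1 with 2.4.2 at X = 1 does not show that the authors intended something else. Agreed. The stronger internal comparison is SAP 4.4, where additional exploratory subgroup models contain treatment, the subgroup variable and their product.

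Fifth, recipient samples depend on leftover blood or an extra tube, and the documents do not confirm that all four markers are assayed in SOC patients. The printed model can keep an SOC patient with no M^P; a corrected one must exclude or impute. This is a real cost and belongs in the fix.

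**Conclusion.** The model is wrong as written for γ₃. The omission is not typographical shorthand, because only the provider factor is declared suppressed. The reason SAP 4.6.1 gives for dropping main effects does not extend to a patient covariate sampled in both arms. The algebra needs no assumption about prognosis: γ₃ is the CCP-arm slope (exactly so without the provider factor).

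The size does depend on prognosis. The false-positive rate runs from the nominal 5% at an OR of 1.00 to about 20% at 0.91, 59% at 0.83 and 99% at 0.67 per SD, and genuine modification in the opposite direction can be hidden. The primary analysis, the donor-marker models in Supplement 2.2 and 2.3, γ₄ and the serostatus subgroup estimates are untouched. The change should be made, but it is not critical to the trial's main conclusion.

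**What to change.** In Supplement 2.4.2 replace the linear predictor with γ₀ + γ₁X + γ₅M^P + γ₂X·M + γ₃X·M^P + γ₄X·M·M^P, keep the provider factor, and state that γ₃ in this model is the test of modification by the recipient's marker. Make the same change in any multi-marker extension. In SAP 4.6.1, say that recipient markers enter as main effects as well as in products with treatment, and that the omission of main effects applies to donor titres only.

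Also state how missing recipient markers are handled in each arm, since Supplement 1.7 deals only with plasma-unit volumes and markers, and confirm which markers are assayed in SOC patients.

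The cost is one coefficient and a larger standard error for γ₃. By the approximation above, the SOC slope adds 1/(400 × 0.3 × 0.7) = 1/84 to the variance, so the SE rises from 0.085 to √(1/139.5 + 1/84) = 0.138, about 1.6 times. That is the precision the trial actually has on this question. No new sampling is needed beyond what footnote 9 of the schedule already plans, provided the SOC samples are assayed.
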